Summary Table of Study Protocol

Title	An Observational Study to Assess the Effectiveness of the Neulasta® Patient Alert Card and to Measure Medication Errors Related to the Use of the Neulasta® On-Body Injector	
Protocol version identifier	Amendment 1	
Date of last version of the protocol	09 January 2019	
EU Post Authorisation Study (PAS) Register No	Not yet available	
Active Substance	Pegfilgrastim	
Medicinal Product	Neulasta® administered through the on-body injector (OBI)	
Product Reference	EMEA/H/C/000420	
Procedure Number	NA	
Joint PASS	No	
Research Question and Objectives	 The study aims to address the following research questions: Has the implementation of the Patient Alert Card (PAC) as an additional Risk Minimisation Measure (aRMM) been conducted as planned? What is the level of respondent awareness and behavioural intent to act as recommended in the PAC? What is the rate of medication errors observed in routine clinical practice? The primary objective of the study is: To assess respondent awareness of key safety messages and behavioural intent to carry out recommended actions as described in the PAC. The secondary objectives of this study are: To determine if the respondent received the PAC. To estimate the proportion of OBI administrations associated with medication error. 	
Countries of Study	To be determined based on EU countries in which the OBI is approved and utilized. A preliminary list includes Germany, Slovakia, Netherlands, and/or UK.	
Author	PPD , PharmD, MSc Real-World Evidence Solutions, IQVIA [name] Email: PPD MSc PhD Centre for Observational Research, Amgen [name] Telephone: PPD Email: PPD	

Product: Pegfilgrastim Protocol Number: 20170701 Date: 10 April 2019

Date: 10 April 2019 Page 2 of 61

Marketing Authorisation Holder

Marketing authorisation holder(s)	Amgen Europe B.V. [name].
MAH Contact	PPD MSc PhD Centre for Observational Research, Amgen [name] Telephone: PPD Email: PPD

Date: 10 April 2019 Page 3 of 61

Confidentiality Notice

This document contains confidential information of Amgen Inc.

This document must not be disclosed to anyone other than the site study staff and members of the Institutional Review Board/Independent Ethics Committee/Institutional Scientific Review Board or equivalent, as applicable.

PAS	Post Authorisation Study	
PRAC	Pharmacovigilance Risk Assessment Committee	
PT	Preferred Term	
SAP	Statistical Analysis Plan	
SDLC	System Development Life Cycle	
SmPC	Summary of Product Characteristics	
SMQ	Standardised MedDRA Query	
SOC	System Organ Class	
SOP	Standard Operating Procedure	

Date: 10 April 2019 Page 10 of 61

3. Responsible Parties

MAH	Amgen is the MAH which oversees MAH activities and facilitates Competent Authority submissions.
MAH Representative	The MAH representative for this study is IQVIA, a Clinical Research Organisation (CRO) delegated to serve as the study coordinating centre and conduct the study on behalf of Amgen. The MAH representative will be responsible for overall conduct, deliverables and timelines for the study and communication with Amgen.

4. Abstract

Product: Pegfilgrastim

Study Title

An Observational Study to Assess the Effectiveness of the Neulasta[®] Patient Alert Card and to Measure Medication Errors Related to the Use of the Neulasta[®] On-Body Injector.

Study Background and Rationale

Amgen received a positive opinion recommending a label variation for Neulasta® (pegfilgrastim) to include the Neulasta Onpro® Kit from the Committee for Medicinal Products for Human Use (CHMP) of the European Medicines Agency (EMA) in February 2018. The Neulasta Onpro[®] Kit consists of one pre-filled syringe with Neulasta and an on-body injector (OBI) delivery system. While every OBI undergoes a thorough quality control process before being distributed into the market, issues such as leakage, the device coming loose from the skin, or other device issues, may occur. These device issues can result in medication errors which are defined as an 'unintended failure in the drug treatment process that leads to, or has the potential to lead to, harm to the patient' (EMA, 2015). "Medication errors including underdose-On-body Injector, resulting in lack of efficacy" is an important identified risk in the Neulasta EU Risk Management Plan. An additional risk minimization measure (aRMM) in the form of a Patient Alert Card (PAC) has been developed to further support patients in the safe and appropriate use of the Neulasta OBI. The PAC is required to be distributed to all HCPs who place an order for Neulasta OBI as agreed with local health authorities according to local requirements. In line with regulatory guidance, aRMMs are required to be evaluated for their effectiveness. The proposed study is intended to evaluate the process of implementation and effectiveness of the aRMMs for the OBI by assessing the respondent awareness of key safety messages and their behavioural intent to implement recommended actions as described in the PAC.

Date: 10 April 2019 Page 11 of 61

Research Question and Objective(s)

- Primary Objective
 - To assess respondent awareness of key safety messages and behavioural intent to carry out recommended actions as described in the PAC.
- Secondary Objectives
 - To determine if the respondent received the PAC.
 - To estimate the proportion of OBI administrations associated with medication error.
- Hypothesis/Estimation
 - This is an estimation study. No formal hypothesis will be tested. Results will be presented as estimates with 95% confidence intervals as measures of precision.

Study Design/Type

An observational cross-sectional study is planned in a number of EU countries after the introduction of the OBI for Neulasta in the EU market.

Study Population or Data Resource

The source population will be the primary person responsible for monitoring the OBI after application, ie, patients or, if appropriate, their caregivers. This person will be defined as the "respondent". For every patient receiving OBI for Neulasta, the respondent will be defined at the time of study inclusion. Respondents can be included in the study multiple times at different chemotherapy cycles in which the OBI is being prescribed to the patient, if eligibility criteria including informed consent are met. In subsequent administrations of the questionnaire, data will only be collected to meet the secondary objective regarding medication errors (via a partial respondent questionnaire).

HCPs working at sites in which the OBI is being prescribed or expected to be prescribed will be approached for participation in the study.

Summary of Subject Eligibility Criteria

- Inclusion criteria
 - Respondent (ie, patients or caregivers primarily responsible for monitoring the OBI) who agrees to be contacted for the questionnaire.
 - Respondent aged 18 or more years.
 - Respondent with no cognitive impairment.
 - Respondent who can read and understand the language in which the study is being conducted and in which the PAC is provided.

Date: 10 April 2019 Page 12 of 61

Patient has been prescribed the OBI for Neulasta delivery for their current chemotherapy cycle.

Patient and respondent provide their written informed consent to participate in the study.

Exclusion criteria

Product: Pegfilgrastim

- Respondent personally works, or works on a consultancy basis, for any pharmaceutical company or advertising/research agency.
- Patient has participated or is participating in a clinical trial of Neulasta administered via OBI.

Follow-up

No follow-up is conducted after the questionnaire administration in this cross-sectional study.

Variables

- Respondent demographics and characteristics, including age, sex, educational level, self-reported language skills, self-reported confidence to monitor the OBI, health literacy - using the guestions from the Brief Health Literacy Screen (BHLS) questionnaire (Chew et al. 2004) -, respondent type (patient or caregiver)
- Respondent prior use and/or monitorisation of the Neulasta OBI
- Details of respondent receipt and use of the PAC
- Respondent reported awareness of key safety messages in the PAC
- Respondent reported behavioural intent to carry out recommended actions as described in the PAC
- Device issues experienced by the patient (eg, whether the device came loose, red light came on, leakage, etc.) and any resulting actions
- Symptoms of adverse events experienced by the patient (eg, fever, chills, sweating, etc.) and related consultations with HCPs
- Details on dose delivery (eq. expected dose delivered on time, partial dose received, etc.)
- Occurrence of a replacement granulocyte colony stimulating factor (G-CSF) dose (eg, type of replacement and timing)

In addition, the HCP will report the following variables through an electronic case report form (eCRF), to be completed at the time of respondent identification and consent:

- HCP and site characteristics (only reported once per HCP)
- HCP awareness of methods to obtain the PAC

Date: 10 April 2019 Page 13 of 61

Date and time of OBI application

Device issues observed by the HCP at the time of OBI application (eg, the device coming loose, problems filling the device, leakage, etc.)

Study Sample Size

Product: Pegfilgrastim

This study aims to include approximately 80 respondents, however, the final sample size will ultimately depend on the uptake of the OBI in participating countries and willingness of respondents to participate. Expected OBI use in Europe is <10,000 patients per year, therefore, a sample size of 80 respondents is considered feasible.

Assuming patients will use the OBI on average 3.5 times during a single chemotherapy course, 80 independent patients are estimated to receive a maximum of 280 OBI applications.

Data Analysis

All the respondents participating in the study who meet the eligibility criteria will be included in the sample of respondents in which awareness of key safety messages and behavioural intent to carry out recommended actions as described in the PAC will be assessed. These outcomes will be assessed for the first monitored OBI application only.

Distribution of the PAC, awareness of key messages in the PAC and behavioural intent to carry out recommended actions as described in the PAC will be described at respondent level, providing the percentage of correct responses. A success measure will be used to define the success of the PAC.

All OBI administrations reported by participant respondents will be included in the sample of treatments to estimate the proportion of OBI administrations associated with medication error. OBI administrations for Neulasta doses that have not been delivered (due to medication errors) will be also included in the full analysis set of OBI administrations. More than one OBI administration can be reported for the same respondent.

An interim analysis is planned to be performed at 1 year after the start of data collection.

5. **Amendments and Updates**

None.

Date: 10 April 2019 Page 14 of 61

6. Milestones

Milestone	Planned date
Start of data collection	Approximately August 2019*
End of data collection	Approximately July 2021*
Interim analysis	Approximately July 2020*
Registration in the EU PAS register	Approximately April 2019*
Final report of study results	Approximately July 2022*

These timelines are subject to the timely launch of the OBI in participating countries and timely approvals from national competent authorities and ethics committees.

7. Rationale and Background

7.1 Diseases and Therapeutic Area

Amgen received a positive opinion recommending a label variation for Neulasta® (pegfilgrastim) to include the Neulasta Onpro® Kit from the Committee for Medicinal Products for Human Use (CHMP) of the European Medicines Agency (EMA) in February 2018. The Neulasta Onpro[®] Kit consists of one pre-filled syringe with Neulasta and an on-body injector (OBI) delivery system. Neulasta (pegfilgrastim) is approved for use in the European Union (EU) for the reduction in the duration of neutropenia and the incidence of febrile neutropenia in adult patients treated with cytotoxic chemotherapy for malignancy (with the exception of chronic myeloid leukaemia and myelodysplastic syndromes). Neulasta® is to be administered at least 24 hours after cytotoxic chemotherapy (Neulasta EU SmPC), and often requires the patient to return to the healthcare facility for this purpose (Mahler et al. 2017). The Neulasta Onpro® Kit includes a specifically designed Neulasta pre-filled syringe along with a single use OBI. The small, lightweight OBI is applied to a patient's skin on the same day of chemotherapy. The OBI eliminates the burden to return to a healthcare setting for patients and physicians (Mahler et al. 2017), and is a preferred option for approximately 50% of the physicians when considering clinically compromised patients in the need of receiving Neulasta (Hauber et al. 2018).

The OBI is a device that must be filled with Neulasta by an HCP using a pre-filled syringe and then applied to the patient's skin (abdomen or back of arm). The back of the arm may only be used if there is a caregiver available to monitor the status of the OBI for Neulasta. The OBI has a timed mechanism to deliver a subcutaneous injection of Neulasta 27 hours after the device is applied to the patient's skin. The Neulasta dose will be delivered over approximately 45 minutes. The OBI can be applied on the same day as the administration of cytotoxic chemotherapy, if application is timed to ensure the

Product: Pegfilgrastim

Date: 10 April 2019 Page 15 of 61

OBI delivers Neulasta at least 24 hours after administration of cytotoxic chemotherapy (Neulasta EU SmPC).

While every OBI undergoes a thorough quality control process before being distributed into the market, issues such as leakage, the device coming loose from the skin, or other device issues, may occur. These device issues can result in medication errors which are defined as an 'unintended failure in the drug treatment process that leads to, or has the potential to lead to, harm to the patient' (EMA, 2015). Examples for medication errors that may occur as the result of an issue with the device are missed or partial doses of pegfilgrastim which put patients at increased risk of a serious infection if a replacement dose isn't administered.

"Medication errors including underdose-On-body Injector, resulting in lack of efficacy" is an important identified risk in the Neulasta EU Risk Management Plan. In the clinical trial setting, no adverse events within the MedDRA Medication errors Standardised MedDRA Query (SMQ) were reported in 262 subjects who received at least 1 dose of pegfilgrastim via the OBI and among 339 subjects administered placebo via the OBI, 1 subject (<1%) experienced a medication error. A recent study that specifically evaluated the performance of the OBI device in healthy subjects reported that 292 of 297 administrations (98.3%) were successful, while five were considered unsuccessful: two due to hazard alarms, and three due to substantial leakage (Joshi et al. 2017).

Cases of medication errors including underdose events have been reported in the US post-marketing setting after approval of OBI in December 2014. Cumulatively through 31 January 2018, the most frequently reported medication error events in the post marketing setting were events with the preferred terms "wrong technique in product usage process", "drug dose omission", and "underdose".

Risk minimisation activities to address medication errors involve routine measures (eg. product label, Instructions for Use and the Patient Leaflet), as well as an aRMM in the form of a PAC that further supports patients in the safe and appropriate use of the Neulasta OBI. The PAC is printed in color on a wallet sized tri-fold card, and is intended for patients to keep with them as a reference.

Page 16 of 61

Protocol Number: 20170701 Date: 10 April 2019

Specifically, the PAC highlights important messages which are also included in the Package Leaflet - Instructions for Use that are directly related to the following. These messages represent the 'core content' of the PAC that will be assessed as part of this evaluation study:

- 1. When to expect the dose delivery of Neulasta to begin;
- 2. That the OBI should not be removed until after dose delivery is complete;
- How to recognise signs that there may have been a failure in the delivery of the intended dose of Neulasta;
- 4. What actions to take in a suspected case of failed delivery or incomplete delivery of the dose:
- 5. What actions to take if symptoms of serious infection present (ie, the need to immediately contact his/her HCP and how that HCP can be reached).

The PAC includes illustrations of 4 scenarios of possible failed or incomplete administration of Neulasta via the OBI which the patient should recognise:

status light flashes red;

Product: Pegfilgrastim

- adhesive is wet and/or device drips;
- device comes loose, and;
- fill indicator does not indicate empty after the expected time of dose delivery.

The PAC underwent an iterative process of design and piloting, with patient and carer assisting in the co-creation of the final version. The final pilot-tested version is presented in Appendix E.

The PAC is required to be distributed to all HCPs who place an order for Neulasta OBI as agreed with local health authorities according to local requirements. The goal of the PAC is to communicate to patients at each application of the on-body injector how to monitor the on-body injector and recognize signs of device failure that may result in incomplete or failed dose delivery and the appropriate action to be taken.

7.2 **Rationale**

In line with regulatory guidance (EMA, 2014), aRMMs are required to be evaluated for their effectiveness. Additionally, following recommendations from the Committee for Medicinal Products for Human Use and the Pharmacovigilance Risk Assessment Committee (PRAC) review of the marketing authorisation application for the OBI, this study was developed to measure the rate of medication errors.

Date: 10 April 2019 Page 17 of 61

Amgen has developed the protocol for this study in accordance with the requirements of Good Pharmacovigilance Practice (GVP) Modules V (EMA, 2017), VIII (EMA, 2016) and XVI (EMA, 2014), the recommendations provided by the Council for International Organisations of Medical Sciences (CIOMS, 2014) Working Group IX, and an established public health model, the Theory of Reasoned Action (Fishbein 2008), which posits that the antecedents of individual behaviour change are knowledge and behavioural intent.

The proposed study is intended to evaluate the process of implementation and effectiveness of the aRMMs for the OBI by assessing the respondent awareness of key safety messages and their behavioural intent to implement recommended actions as described in the PAC.

7.3 Statistical Inference (Estimation or Hypothesis)

This is an estimation study. Due to sample size limitations, no formal hypothesis will be tested. Results will be presented as estimates with 95% confidence intervals as measures of precision.

8. Research Question and Objectives

The study aims to address the following research questions:

- Has the implementation of the PAC as an aRMM been conducted as planned?
- What is the level of respondent awareness and behavioural intent to act as recommended in the PAC?
- What is the rate of medication errors observed in routine clinical practice?

8.1 Primary

The primary objective of the study is to assess respondent awareness of key safety messages and behavioural intent to carry out recommended actions as described in the PAC.

8.2 Secondary

The secondary objectives of this study are:

- To determine if the respondent received the PAC.
- To estimate the proportion of OBI administrations associated with medication error.

8.3 Exploratory

The exploratory objective of this study is to describe the proportion of device issues at the time of OBI application.

Product: Pegfilgrastim

Date: 10 April 2019 Page 18 of 61

9. **Research Methods**

9.1 Study Design

An observational cross-sectional study based on primary data collection is planned in a number of EU countries after the introduction of the OBI for Neulasta in the EU market.

The source population will be the primary person responsible for monitoring the OBI after application by the HCP, ie, patients or, if appropriate, their caregivers. This person will be defined as the "respondent". For every patient receiving OBI for Neulasta, the respondent will be defined at the time of study inclusion. In case the caregiver is identified as the respondent, the caregiver will need to be present at the time of OBI application and study inclusion.

Participating HCPs will assess the eligibility of respondents in a consecutive manner according to the date of OBI application. This approach is designed to minimise selection bias and to allow for the study results to be generalizable to the wider population of OBI treated patients. Upon patient and respondent consent to participate in the study, the HCP will immediately record in the study electronic case report form (eCRF) the information of the time and day of OBI application. Respondents will be contacted from approximately 27 to 72 hours after the OBI application (ie, approximately 0 to 45 hours after the Neulasta dose is expected to be delivered through the OBI) and asked to respond to a questionnaire. The questionnaire will be administered either by paper or online. Additionally, HCPs will be requested to provide data on their observations (eg, time and date of OBI administration, medication errors at the time OBI application, etc.) at each application of OBI for a participating patient in the eCRF.

Respondents can be included in the study multiple times at different chemotherapy cycles in which the OBI is being prescribed to the patient, if eligibility criteria including informed consent are met (Section 9.2.3). In subsequent administrations of the questionnaire, data will only be collected to meet the primary objective regarding medication errors (via a partial respondent questionnaire).

In case that for a unique patient, the respondent is different in subsequent administrations of the questionnaire (ie, from patient to caregiver, from caregiver to patient, or from caregiver to another caregiver), the new respondent would still be eligible if all eligibility criteria are met, but a full questionnaire would need to be filled in and he/she will be treated as a new respondent. The HCP will check at the time of study inclusion if the respondent identified has been included in a previous OBI administration, to avoid double counting of respondents.

Product: Pegfilgrastim

Date: 10 April 2019 Page 19 of 61

The number of potential respondents screened but not enrolled into the study will be recorded.

9.2 **Setting and Study Population**

The study is planned to be conducted in a number of EU countries in which the OBI is approved and utilized. A selection of EU countries are planning launching the OBI over the period of 2018 and 2019. Based on the current forecasted launch timetable, a preliminary selection of countries for this study is likely to include Germany,

Netherlands, Slovakia and/or UK. The final selection of countries will be informed by a country level feasibility assessment and will correspond to a combination of expected product uptake, adequate timing of the product launch and logistical barriers foreseen to allow for the completion of the study within the required timeframe, with a minimum of 2 different EU countries represented.

This rationale is based on factors that may change as the study progresses (ie, initial usage forecasts and planned launch schedule). Therefore, if recruitment of respondents is slower than anticipated other countries and/or sites may be added to meet sample size goals within the study timeline.

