Awareness of key safety messages and behavioural intent to carry out recommended actions as described in the PAC: will be evaluated using a set of multiple choice questions included in the questionnaire. A composite score for each individual will be calculated based on the proportion of all awareness and behavioural intent questions with correct responses.

The secondary endpoints for the respondent questionnaire are:

- Receipt of the PAC by the respondent: a categorical variable will describe if the respondent received the PAC.
- Medication errors with OBI administrations. The proportion of total OBI administrations with medication errors with respect to total OBI administrations, and the total number of patients will be calculated.

Measure of Success

The results of the study will be interpreted considering an acceptable level of patients and/or caregivers awareness and behavioural intent. The study estimates and associated 95% confidence intervals (CIs) will be evaluated in the context of a desired population-level threshold of at least 70%. The selection of a threshold for success is subjective and not based on a priori knowledge, experience, or established scientific criteria in the education or risk communication or evaluation literature. Therefore, the results will be contextualised with other available information. The appropriateness of the minimum 70% threshold as a measure of success will be reviewed at the time of the 1-year interim analysis.

Table 1. Measures of Success

Description of measure	Assessment
Distribution of the PAC	The threshold of 70% is within the 95% CIs of the proportion of respondents who provide an affirmative response to the key question regarding receipt of the PAC.
Success of the PAC	For the respondents who have received the PAC, the threshold of 70% is within the 95% CIs of the composite score for awareness and behavioural intent

Date: 10 April 2019 Page 23 of 61

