Appendix F. Patient Alert Card

How to monitor the on-body injector

- For the first 27 hours you are wearing the on-body injector, you should see a slow flashing green light.
- Two minutes before dose delivery begins, you will hear a series of beeps.
- When dose delivery begins, you will see a fast green light.
- The dose will take 45 minutes to deliver.
- When the delivery is done, you will hear a long beeping sound and the status light will be solid green.
- Now, slowly pull off the on-body injector. Check to see if it is empty.
- Call your healthcare professional immediately if you have any issues with the on-body injector, or symptoms of infection such as fever, chills or sweating.
- Do not try to secure the on-body injector if it becomes loose or try to reapply it.

Neulasta® (pegfilgrastim)

On-body Injector Patient Alert Card

- Please open this card and read both sides.
- Keep it with you.
- This card contains important safety information that you need when receiving treatment with the peofilgrastim on-body injector.
- Show this card to your healthcare professional if you need to seek urgent medical advice for the on-body injector.

Dated December 2017

Important information

The purpose of this card is to help prevent medication errors - mainly, drug underdose.

- A drug underdose may happen if the on-body injector comes loose from your skin, leaks, or otherwise malfunctions.
- If that happens, you may be at increased risk of a serious infection.

For more information:

- Read the Package Leaflet that comes with your on-body injector.
- Visit the European Medicines Agency (EMA) website (http:bit.ly/2kt26wk) and/or local equivalent websites.

The following activities may interfere with the on-body injector's performance:

- Do not knock or pull the on-body injector.
- Do not get lotions, creams, oils or cleaning agents near the on-body injector.
- Do not sleep on the on-body injector. or apply pressure during wear.
- Do not expose the on-body injector. to CT scan, MRI, x-ray, ultrasound, radiation treatment, or hyperbaric chambers.
- Do wear loose clothing and be careful when changing clothes.
- Do keep the on-body injector at least 10 cm (4 inches) away from electrical equipment (such as mobile phones or microwaves).

Please read this card and keep it with you

This information should be completed by your healthcare professional

Your on-body injector was applied to your skin:

Day Time AM / PM

Your dose delivery will start around:

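### Awareness is measured almost entirely after dose delivery, so items on message 1 and partly message 2 may be answered from watching the device, and the 70% reading uses only a composite that includes them

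*Protocol*

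**What the plan says.** **Timing.** Protocol section 9.1: "Respondents will be contacted from approximately 27 to 72 hours after the OBI application", which the same sentence restates as "approximately 0 to 45 hours after the Neulasta dose is expected to be delivered through the OBI". Section 7.1 says the injector is timed to "deliver a subcutaneous injection of Neulasta 27 hours after the device is applied to the patient's skin" and adds: "The Neulasta dose will be delivered over approximately 45 minutes".

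**Content.** Section 7.1 lists five core messages to be assessed. The first is "When to expect the dose delivery of Neulasta to begin" and the second is "That the OBI should not be removed until after dose delivery is complete". Messages 3 to 5 cover signs of failed delivery, what to do about it, and what to do about symptoms of infection. Section 9.3 gives delivery alerts and the time of removal as examples of awareness items.

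**What the device shows.** According to the card in Appendix F, the injector beeps two minutes before delivery and flashes fast green at the start. At the end: "When the delivery is done, you will hear a long beeping sound and the status light will be solid green".

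**Scoring.** Section 9.3.2: "A composite score for each individual will be calculated based on the proportion of all awareness and behavioural intent questions with correct responses". Table 1 judges the success of the card by reading this composite, among respondents who received the card, against 70%.

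**Related analyses.** Section 9.7.2.4 also plans results by individual question, and the composite by card receipt, prior OBI administrations and health literacy. Section 9.7.2.5 plans no sensitivity analysis. Section 9.9.1.2 mentions the 72-hour limit only as helping against recall bias. Nothing in section 9.9 mentions learning from the delivery just observed.

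**The concern.** The success reading attributes the score to the card. A respondent who has just monitored a delivery has heard the beeps, seen the lights change and taken the device off. That person can answer an item on when delivery begins without having read the card, and may be helped on an item about removal. The score then mixes what the card taught with what the device showed, and for these items the error would be upward.

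The planned subgroups do not separate the two sources. First-time respondents have also watched a delivery before they answer, so the split by prior OBI use does not isolate the effect. Respondents without the card have watched the same device, so the split by receipt tends to understate what the card adds on these items.

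At stake is the conclusion on whether the card works as a risk minimisation measure. The messages about recognising failure and acting on it are not taught by an uneventful delivery, and a composite helped by messages 1 and 2 could hide weak knowledge of them.

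**Working it through.** **1. Where the window lies.** Delivery ends at about 27 + 45/60 = 27.75 h. The window runs from 27 to 72 h, which is 45 h. The part after delivery is 72 − 27.75 = 44.25 h. Only the first 0.75 h overlaps with delivery.

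**2. The plan's own precision figure.** Table 2 gives a half-width of 0.10 for a proportion of 0.7 with 80 respondents. Check: 1.96 × √(0.7 × 0.3 / 80) = 0.1004. All 15 rows of Table 2 reproduce to two decimals. The table is for a proportion, whereas the composite is a mean of individual scores with no SD given, so this is only a yardstick.

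**3. Size of a possible lift (illustration).** Let
- p = share of items known before delivery, taken as equal for all items,
- w = share of items on the messages the device shows,
- f = fraction of those who did not know who learn it from the device.

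Observed composite = p + w·f·(1 − p). None of p, w and f is in the protocol. If items are spread evenly over five messages, w = 0.2 for message 1 alone and 0.4 for messages 1 and 2.

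| p | w | f | Observed |
|---|---|---|---|
| 0.50 | 0.2 | 1 | 0.50 + 0.2 × 0.50 = 0.60 |
| 0.50 | 0.4 | 0.5 | 0.50 + 0.4 × 0.5 × 0.50 = 0.60 |
| 0.50 | 0.4 | 1 | 0.50 + 0.4 × 0.50 = 0.70 |
| 0.60 | 0.2 | 1 | 0.60 + 0.2 × 0.40 = 0.68 |
| 0.60 | 0.4 | 1 | 0.60 + 0.4 × 0.40 = 0.76 |

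For p = 0.50, w from 0.1 to 0.5 and f from 0 to 1, the lift runs from 0 to 0.5 × 1 × 0.5 = 0.25, that is 0 to 25 points.

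**4. The same thing read backwards.** If messages 1 and 2 reach 100% and carry weight 0.4, a composite of 70% needs only x on messages 3 to 5, where 0.4 × 1.0 + 0.6x = 0.70, so x = 0.50. If messages 1 and 2 reach 90%, 0.4 × 0.9 + 0.6x = 0.70 gives x = 0.567.

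**5. Could it touch the success reading?** With n = 80 and the Table 2 approximation, 70% lies within the CI for observed values of about 0.593 to 0.789. With f = 1, an observed 0.593 corresponds to prior knowledge of (0.593 − 0.2)/0.8 = 0.49 if w = 0.2, and (0.593 − 0.4)/0.6 = 0.32 if w = 0.4. The rule applies to card recipients, who may number fewer than 80. Taken literally, it is also not met when the whole CI lies above 70%; that is a separate matter.

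**The case against.** The case against is substantial.

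- **Item-level results are planned.** Section 9.7.2.4 analyses individual questions and section 9.7.2.1 provides 95% CIs for outcome variables. A reader of the report will be able to see messages 1 and 2 apart from the rest, and how items are grouped can be left to the SAP. This stands, and it narrows the point to the 70% reading, which section 9.3.2 ties to the full composite alone.
- **The target is awareness, not awareness before delivery.** Section 8.1 sets no time point. Experienced users are enrolled by design, and the messages also appear in the Package Leaflet, so the study never isolates one source of knowledge. This stands as a description of the design. Table 1 nevertheless labels the reading as success of the card.
- **The threshold is not rigid.** The protocol calls it subjective, says results will be put in context, and reviews it at the interim. That argues for giving the reader a second figure as context, not against it.

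A reader might infer stronger claims that the protocol does not support.

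- *That awareness is measured only after the full cycle.* The window opens as delivery starts. Under section 9.6 the respondent receives the paper form and the link from the HCP beforehand, and no stated step prevents early completion.
- *That message 2 is demonstrated in the same way as message 1.* It is a prohibition. The device signals completion but does not state the rule, and a failed or interrupted delivery may show neither message.
- *That the composite is inflated as a matter of fact.* The questionnaire is a stand-alone document (Appendix A), so the number and wording of items per message are unknown. Behavioural-intent items also enter the score, which may make the share on messages 1 and 2 smaller than 0.4. The lift could be near zero.
- *That inflation is largest where the device failed.* This is conjecture. At the failure rate cited in section 7.1 (5 of 297), 80 first applications would yield about 80 × 5/297 = 1.3 failures, too few to support a separate analysis.

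**Conclusion.** The point holds in limited form. The planned timing puts almost all awareness measurement after delivery. The device directly shows the content of message 1 and part of message 2. These items feed the only score read against 70%, and the protocol neither acknowledges the possible effect nor plans an analysis without them.

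The likely direction is upward; the size cannot be determined from the protocol. Under even weighting and 50% prior knowledge, the lift is 10 points if message 1 alone is fully taught and 20 points if both are. The first is about as large as the Table 2 half-width at 80 respondents, so a lift of that order could change how the result is read. Both figures assume equal prior knowledge across items and complete learning by those who did not know. They illustrate the possible size and are not estimates.

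The timing itself is not at fault. The same questionnaire collects dose delivery, device issues and replacement doses, which can be answered properly only after delivery.

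**What to change.** Keep the 27 to 72 hour window and the single questionnaire.

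1. In sections 9.7.2.4 and 9.7.2.5, pre-specify a supportive composite that excludes the items on messages 1 and 2, and list those items before any data are reviewed. Report it with its 95% CI, shown against the 70% threshold beside the full composite, in the same respondents.
2. In section 9.9.1.2, add that respondents may have learned the content of message 1, and partly of message 2, from the delivery they had just observed, and that this may raise their scores.

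The cost is one derived variable, one table row and a sentence or two of text; no new data are needed. The downside is that the reduced score rests on fewer items and may be less favourable. No separate analysis by device issue is needed for this point.
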